6.3.6 ACR-28 Joint Count

The ACR-28 joint count will evaluate the number of tender and swollen joints in the shoulder, elbow, wrist, hand, knee joints. Joints of the feet are excluded.

6.4 Other Variables

6.4.1 SLICC/ACR Damage Index

The SLICC/ACR damage index is a validated instrument to assess damage, defined as irreversible impairment, continuously persistent for 6 months (ascertained by clinical assessment), occurring since the onset of lupus, and it is based on a weighted scoring system. This index records damage occurring in patients with SLE regardless of cause, with demonstrated content, face, criterion, and discriminant validity.⁴⁹ It will be performed on Days 0 and 180.

6.4.2 PROs

Patients should be encouraged to complete the PROs at the clinic at the beginning of the study visit prior to any clinical assessments. A member of the staff should be available if a patient requires further instruction and to review the PRO questionnaires for completeness prior to leaving the clinic. The PROs include the CCI and the CCI and will be assessed as specified in the Schedule of Assessments (Section 3.4).

CCI

50

CCI

6.5 Pharmacokinetic Assessments

During the MAD Phase 1b (all sites) and POC Phase 2 (select sites only) parts of the study, blood samples for PK analysis of BOS161721 or placebo concentration will be collected according to Table 1 and Table 2.

Plasma concentrations of BOS161721 will be measured using a validated immunoassay. The PK parameters will be calculated from the plasma concentration actual time profiles.

6.6 Pharmacodynamic Assessments

Blood samples for PD parameters (plasma) will be collected at times indicated in the Schedule of Assessments (Section 3.4) for each of the following parameters:

- pSTAT3 (predose [trough] samples only Phase 1b)
- Antibodies: CCI
- Plasma complement (CCI)

- Plasma CCI and CCI
- Whole blood for leukocyte immunophenotype

6.7 Pharmacokinetic/Pharmacodynamic Relationship

Evidence of any PK/PD relationships will be evaluated between BOS161721 plasma concentrations and the available PD endpoints and biomarkers.

6.8 Protocol Deviations

Protocol deviations will be documented during the study.

7 STUDY DRUG MANAGEMENT

7.1 Description

7.1.1 Formulation

CCI

CCI

Additional information regarding dose preparation will be provided in a separate Pharmacy Manual.

7.1.2 Storage

All supplies of BOS161721 or placebo must be stored in accordance with the manufacturer's instructions. BOS161721 or placebo will be stored in a securely locked area, accessible to authorized persons only, until needed for dosing.

Information regarding storage and dose preparation will be provided in a separate Pharmacy Manual.

7.2 Packaging and Shipment

Investigational medicinal products will be supplied by Boston Pharmaceuticals, Inc. Investigational medicinal products will be packaged and labeled according to applicable local and regulatory requirements.

7.3 Dose and Administration

Details of dosing are provided in [Section 3.1](#).

Each unit dose will be prepared by a qualified staff member. The vials of investigational product (IP) will appear identical and will have a "blinded" label on the vials that will state [REDACTED] mg or placebo. When the site goes into the IWRS to request the patient kit(s), the IWRS will assign the appropriate number of kits (regardless of assignment to placebo or active treatment) per the dose (ie, [REDACTED]). If a patient is randomized to the placebo arm, they will receive the matching number of kits.

The designated staff member (or designee under the direction of the designated staff member) will dispense BOS161721 or placebo for each patient according to the protocol, randomization list, and Pharmacy Manual, if applicable.

After receiving sponsor approval in writing, the investigational site is responsible for returning all unused or partially used BOS161721 or placebo to the sponsor or designated third party or for preparing BOS161721 or placebo for destruction via incineration.

Further details are found in a separate Pharmacy Manual.

7.4 Accountability

The Principal Investigator or designee is responsible for maintaining accurate accountability records of BOS161721 or placebo throughout the clinical study. The drug accountability log includes information such as, randomization number, amount dispensed and amount returned to the pharmacy (if any). Products returned to the pharmacy will be stored under the same conditions as products not yet dispensed. The returned products should be marked as 'returned' and kept separate from the products not yet dispensed.

All dispensing and accountability records will be available for sponsor review after database lock procedures are completed. During safety monitoring, the drug accountability log will be reconciled with the products stored in the pharmacy.

7.5 Prohibited Concomitant Therapy

Prohibited concomitant medications are discussed in [Section 4.6](#) and [APPENDIX 4](#) and will be listed as protocol violations if taken when not permitted.

7.6 Compliance

Dosing will be performed by trained, qualified personnel designated by the principal investigator. The date and time of dosing will be documented on each dosing day. Comments will be recorded if there are any deviations from the planned dosing procedures.

8 STATISTICS

The following analyses are planned:

- An IA will be performed during the last cohort of the MAD portion to determine dose selection for the POC part of the study.

- An additional analysis may be performed for the MAD portion of the study when all MAD patients have completed the safety follow-up or withdrawn from the study, and prior to final analysis. Data from the POC part of the study will be excluded from this additional analysis.
- The final analysis will be performed when all patients have completed the POC safety follow-up or withdrawn from the study.
- Safety analyses will be performed for DMC reviews throughout the study to evaluate dose escalation decisions and accumulating safety data. The frequency and details of the content and format of the safety review meetings will be described in the SAP and/or DMC charter.

All statistical analyses will be performed using Statistical Analysis Software (SAS®) Version 9 or higher.

The following standards will be applied for the analysis unless otherwise specified. Data will be summarized descriptively by treatment and overall for each study portion. For the MAD part of the study, BOS161721 will be summarized overall and by each dose level, and placebo patients from each cohort will be combined. Select parameters may be summarized using patients from both study parts. Statistical testing will be performed on data from the Phase 2 portion only.

Continuous data will be summarized using number, mean, standard deviation (SD), 25th and 75th percentiles, minimum, median, and maximum. Categorical data will be summarized by treatment group using frequency tables (number and percentage). Time to event data will be summarized using counts, medians, 25th and 75th percentiles, and standard error. All data will be listed for all patients.

Statistical inference will be based on a 2-tailed test with an overall 0.10 level of significance, unless stated otherwise.

The effects of noncompliance, background therapy use, treatment discontinuations, premature withdrawal from study and covariates will be assessed to determine the impact on the general applicability of results from this study. Exploratory analyses of the data will be conducted as deemed appropriate. Any deviations from the planned analyses will be described and justified in the final integrated CSR.

Protocol deviations and prohibited medications that define medication failures will be fully assigned and documented before database lock and unblinding.

Further details of the analysis, including the handling of missing data, transformations and other data handling procedures will be provided in the SAP.

8.1 Sample Size

Sample size in the Phase 1b part of the study is based on operational consideration.

The sample size in the Phase 2 portion is based on the primary endpoint, SRI-4 Response at Day 210. Approximately 156 additional patients will be randomized in a 2:1 ratio to BOS161721 versus placebo to achieve 132 evaluable patients in the FAS. This assumes

24 patients will drop prior to having received treatment and an evaluable post-baseline efficacy measure. Enrollment and randomization will be monitored in a blinded fashion and increased if needed to ensure at least 132 patients are randomized into the FAS.

A total of 132 patients randomized provides more than 80% power to detect a treatment difference of 25% in SRI-4 response rates at Day 210, based on a targeted 2-sided significance level of 10% and using a 2-sided Pearson's chi-squared test. This assumes of a response rate of 65% for BOS161721 and 40% for placebo, where missing data at Day 210 is carried forward from most recent non-missing result and patients are treated as a non-responder if a prohibited medication defined as a medication failure occurs.

8.2 Statistical Methods

8.2.1 Analysis Populations

The primary efficacy analysis will be based on the FAS, defined as all patients who receive at least 1 dose of study treatment and at have least 1 evaluable post-baseline efficacy evaluation. FAS analyses will be conducted on the basis of the randomized treatment.

A per protocol (PP) analysis set may be defined to exclude major protocol violations from the efficacy analysis. The PP Population will include all patients from the FAS except those with major violations to the protocol deemed to impact the analysis of the primary endpoint. These violations will be identified based on blinded data prior to study unblinding. PP analyses will be conducted on the basis of the randomized treatment.

Safety analyses will be based on the safety analysis set (SS), defined as all patients who receive at least 1 dose of study treatment. Safety analyses will be conducted on the basis of actual treatment received.

Pharmacokinetic analysis will be conducted on the PK analysis set, defined as the FAS with sufficient concentration data for the calculation of PK parameters.

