8.2.6 Pharmacokinetic and Pharmacodynamic Data

8.2.6.1 Analysis of Pharmacokinetic Data

PK parameters will be calculated from concentration data collected during the MAD Phase 1b portion of the study using non-compartmental analysis and include the following:

- C_{max} , T_{max} , AUC, $t_{1/2}$, CL, V_d

The PK parameter data will be listed and summarized descriptively in tabular format.

If data permit, the following analyses will be performed for plasma BOS161721 concentration data:

- A listing of all plasma BOS161721 concentrations by patient at actual times post dose;

- A descriptive summary of plasma BOS161721 concentrations. Summary statistics of geometric mean, % coefficient of variation, standard deviation, median, minimum, and maximum will be tabulated by study days with PK assessments.

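### The PK analysis set is tied to an efficacy visit and to parameter-level sampling, so some usable concentrations fall outside the planned PK summaries

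*Protocol*

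**What the plan says.** Protocol section 8.2.1 sets out the analysis populations. For PK it says "Pharmacokinetic analysis will be conducted on the PK analysis set", and that set is "defined as the FAS with sufficient concentration data for the calculation of PK parameters". The FAS on which it rests is "defined as all patients who receive at least 1 dose of study treatment and at have least 1 evaluable post-baseline efficacy evaluation".

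On treatment basis, the same section says "FAS analyses will be conducted on the basis of the randomized treatment", gives the per-protocol set a randomised-treatment sentence of its own, and says "Safety analyses will be conducted on the basis of actual treatment received". It has no such sentence for PK.

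Section 8.2.6.1 says "PK parameters will be calculated from concentration data collected during the MAD Phase 1b portion of the study using non-compartmental analysis". It then plans, if data permit, a listing of all plasma concentrations and a descriptive summary by study day. Neither of these is limited to MAD. Section 6.5 has PK samples taken at all MAD sites and at selected Phase 2 sites.

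**The concern.** Two membership conditions do not suit a PK set.

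- **An efficacy evaluation.** A concentration is informative once drug has been given and blood drawn. Whether SLEDAI-2K, BILAG or PGA was later scored has no bearing on it.
- **Data sufficient for PK parameters.** This suits a table of Cmax or AUC. It does not suit a table of concentrations by day, which needs only a measurable sample, yet section 8.2.1 provides one set for both.

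At stake are the PK summaries (PK is a secondary MAD objective, section 2.1) and the exposure-response work. Section 8.2.6.3 allows exposure to be related to biomarkers or significant safety endpoints. The safety set holds every dosed patient, so a patient with an early adverse event and early departure can be in the safety set and outside the PK set. The two populations for that analysis would then not match.

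**Working it through.** **1. Timing of samples and efficacy visits (section 3.4, Tables 1 and 2)**

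| Portion | Post-dose PK before Day 30 | First scheduled post-baseline SLEDAI-2K, BILAG, PGA |
|---|---|---|
| MAD | Day 0 at 4, 8 and 24 h; Day 7; Day 15 | Day 30 |
| Phase 2, PK sites | Day 15 | Day 30 |

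Section 1.2.3 gives a median Tmax of 6 days from the single-dose study. A MAD patient who leaves between Day 15 and Day 30 can therefore have samples on both sides of the expected peak, enough for an observed Cmax and Tmax though not for a terminal half-life, and still have no efficacy evaluation.

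**2. Who is actually excluded**

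Leaving before Day 30 is not enough. Section 5.5 asks patients who withdraw after dosing to have an end-of-treatment visit, labelled Day 180, and a last follow-up visit, labelled Day 270. Efficacy scores are scheduled at both. A patient who attends either one can enter the FAS. The exclusion falls on dosed patients with post-dose samples who leave before Day 30 and attend neither visit. They are lost to the PK summaries and parameters, not to the listings: section 8 lists all data for all patients.

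**3. Phase 2 samples**

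Section 8.2.6.1 derives parameters from MAD only. Phase 2 sampling is pre-dose at dosing visits, one post-dose sample on Day 15, and samples on Days 187 to 270. Whether such data meet a condition written in terms of parameter calculation is unclear. For a Phase 2 patient leaving before Day 30, the single Day 15 sample would not support parameters, so the sufficiency clause alone already excludes that patient.

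**4. Size in MAD**

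Active patients by cohort (section 3.1.1): 5, 9 and 9; total 5 + 9 + 9 = 23. One exclusion removes 1/5 = 20% of the 20 mg group, or 1/9 = 11% of the 60 mg or 120 mg group.

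The protocol gives no rate p for the exclusion in step 2. For an assumed range, the expected number lost is 23p and the chance of losing at least one is 1 − (1 − p)^23:

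| Assumed p | Expected lost of 23 | Chance of at least one |
|---|---|---|
| 2% | 0.46 | 37% |
| 5% | 1.15 | 69% |
| 10% | 2.30 | 91% |

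These rows show sensitivity to p; they are not estimates.

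**5. Why the Phase 2 loss figure does not help**

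Section 8.1 assumes that "24 patients will drop prior to having received treatment and an evaluable post-baseline efficacy measure": 156 − 24 = 132, and 24/156 = 15.4%, or 24 × 2/3 = 16 active patients at 2:1. The figure does not separate never-dosed patients, who have no drug levels, from dosed ones. It also covers sites that draw no PK samples.

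**6. Effect on the primary test**

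None. With 88 and 44 patients, 65% versus 40% and two-sided alpha 0.10, power is 0.866, in line with the stated figure of more than 80%. The definition of the PK set does not enter that calculation.

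**The case against.** The strongest reply is that the defect is one of wording and that hardly anyone is affected. Much of this stands.

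- The visits requested in section 5.5 can bring early leavers back into the FAS.
- Sections 4.8.1 and 3.1.1.1 allow MAD patients to be replaced, which refills the group, although it does not recover the departed patient's samples.
- Section 3.1.2.1 reports interim data on all 6, 12 and 12 MAD patients. It does not give doses per patient, but nothing there suggests loss before Day 30.
- Early adverse events are kept, because safety uses all dosed patients.

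Three stronger readings are tempting and are not supported.

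- **PK is analysed as randomised, so mis-dosed patients are shown under the wrong treatment.** The randomised rule is stated for FAS and per-protocol analyses only. The per-protocol set is also a subset of the FAS and gets its own sentence, so the rule is not shown to pass automatically to subsets. The protocol is silent for PK. Only if the PK set inherits the FAS rule would mis-dosed patients be summarised as randomised.
- **Phase 2 concentrations have no analysis set and will go unused.** Only the parameters are limited to MAD. The concentration listing and by-day summary carry no such limit, and sections 8.2.6.2 and 8.2.6.3 plan further use of PK data. The supportable statement is that membership of Phase 2 samples is unclear.
- **About 15% of Phase 2, or 16 active patients, are affected.** This fails for the reasons in step 5 of the working.

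The reply does not remove the core. The efficacy condition and the sufficiency condition are written rules, not silences left for the statistical analysis plan, and the protocol gives no PK reason for either.

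**Conclusion.** The point holds as a small defect in a stated definition. Section 8.2.1 can exclude usable concentrations from the PK summaries because an efficacy evaluation is absent, and its sufficiency condition does not fit concentration-by-day summaries or sparse Phase 2 sampling. The treatment basis for PK is unstated, which is an ambiguity rather than an error.

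The number affected cannot be derived from the protocol and is probably small. The effect of a single case is not negligible in MAD, at 11% to 20% of a planned active dose group if the patient is not replaced. This rests on two assumptions: that at least one dosed patient with post-dose samples leaves before Day 30 and attends no later efficacy visit, and that section 8.2.1 is applied as written. The consequences are confined to PK and exposure-response summaries.

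**What to change.** Replace the PK sentence in section 8.2.1 with two definitions:

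1. **PK concentration set:** all patients in the safety set with at least one measurable post-dose BOS161721 concentration, from either portion, summarised by actual treatment received. Use it for the concentration summaries and the exposure-response work.
2. **PK parameter subset:** MAD patients in the concentration set with enough samples for the parameter in question, judged parameter by parameter, so that a patient can contribute Cmax and Tmax without contributing half-life.

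The cost is one or two sentences. No new data, visits or samples are needed, and sample size, power and alpha do not change.

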8.2.2 Demographics and Baseline Characteristics

Baseline and patient characteristics will be summarized using all randomized patients.

8.2.3 Primary Efficacy Endpoint(s)

The proportion of patients who achieve a SRI-4 response at Day 210 will be assessed via Pearson's chi-squared analysis. The primary efficacy endpoint will be analyzed using the FAS and if needed repeated in the PP analysis set. Missing values will be addressed by employing a last observation carried forward (LOCF) analysis. Other imputation methods may be employed as a sensitivity analysis and will be described in the SAP. Additional analyses exploring impact of baseline factors such as baseline disease severity, race, and other characteristics may be performed.

Patients that received prohibited medications or unallowable CS usage as described in [Section 4.6](#) will be considered "medication failures" and will be treated as non-responders for the

primary efficacy analysis. The determination of medication failures will be reviewed using blinded data and finalized prior to unblinding.

The superiority of BOS161721 relative to placebo will be evaluated. If the proportion of SRI-4 responders for the selected POC dose in BOS161721 arm is higher than that of the placebo arm, then BOS161721 will be considered superior to placebo if the 2-sided p-value is less than 0.10. Secondary and exploratory endpoints for this POC portion will be evaluated based on the same statistical hypothesis.

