3.1.2.2 POC Study Design

For the POC part of the study, approximately 156 additional patients will be randomized to active or placebo groups in a 2:1 ratio.

As in the MAD part of the study, each patient in the POC portion may receive a total of 7 SC monthly doses of study drug on Days 0, 30, 60, 90, 120, 150, and 180. Assessments will be completed according to the Schedule of Assessments ([Section 3.4](#)).

DMC safety reviews will be conducted periodically throughout the study as described in the DMC charter.

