3.2 Randomization and Blinding

This is a randomized, double-blind study.

Patients meeting all inclusion and exclusion criteria will be centrally randomized to either placebo or BOS161721 using an IWRS according to a randomization list generated by an independent, non-study statistician. Randomization will be performed separately for each study portion and separately for each cohort in the Phase 1b and 2 portions as follows:

Phase/Cohort	Number of Patients	Randomization Ratio BOS161721:Placebo
Phase 1b/Cohort 1	6	5:1
Phase 1b/Cohort 2	12	3:1
Phase 1b/Cohort 3	12	3:1
Phase 2	156*	2:1

*Additional patients may be enrolled to ensure sufficient numbers of patients are in the full analysis set (FAS).

[figure not shown]
Eligible patients will be assigned to the study portion which is active at time of enrollment. Similarly, patients in the Phase 1b MAD will be assigned to the cohort which is active. Each patient will be assigned a unique randomization number which will not be reused.

All patients, investigators, and study team participants will be blinded to treatment assignment. An independent biostatistician not otherwise involved on the study will be unblinded and prepare materials for the IA, ad hoc analyses as needed, and the DMC safety reviews. The DMC will

review unblinded data during safety reviews and the IA. A limited team at Boston Pharmaceuticals will review unblinded results from the Phase 1b MAD portion during the IA to determine the dose that will be used for the Phase 2 POC portion of the study. Details regarding maintenance of the blinding and content of data reviews will be described in the DMC charter or related study documentation.

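### The primary SRI-4 test is valid and adequately powered, but it makes no use of the Day 0 SLEDAI-2K score from which response is measured; pre-specifying that adjustment would be a nearly free improvement.

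*Protocol*

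**What the plan says.** Protocol Section 8.2.3 fixes the primary test: "The proportion of patients who achieve a SRI-4 response at Day 210 will be assessed via" a Pearson chi-squared test. It is run in the full analysis set (FAS), with no covariate or stratum. Section 8.1 sizes the trial on the same test, "based on a targeted 2-sided significance level of 10% and using a 2-sided Pearson's chi-squared test", and states that "A total of 132 patients randomized provides more than 80% power to detect a treatment difference of 25% in SRI-4 response rates at Day 210", assuming a "response rate of 65% for BOS161721 and 40% for placebo".

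On allocation, Section 3.1.2.2 says that "approximately 156 additional patients will be randomized to active or placebo groups in a 2:1 ratio". Section 3.2 says that "Randomization will be performed separately for each study portion and separately for each cohort in the Phase 1b and 2 portions". It names no stratification factor within Phase 2.

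Baseline factors appear in two places. Section 8.2.3 says that "Additional analyses exploring impact of baseline factors such as baseline disease severity, race, and other characteristics may be performed". The introduction to Section 8 says that covariates and background therapy will be assessed for their bearing on how generally the results apply. Neither statement changes the primary test.

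The data are already collected: Section 5.2 and Table 2 place SLEDAI-2K and concomitant medication on Day 0.

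**The concern.** Section 6.3.4.1 defines SRI-4 partly by a drop of at least 4 points in SLEDAI-2K, and Section 4.4 admits patients with scores of 6 and above. A patient who enters at 6 must reach 2 or less, whereas one who enters at 14 need only reach 10. The chance of responding may therefore depend on the starting score, which makes that score a natural covariate.

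With about 44 placebo patients and no stratification factor named, the arms can differ by chance on the starting score, and an unadjusted test does nothing about it. Section 8.2.4 allows ANCOVA for continuous secondary endpoints, yet the endpoint that carries the proof-of-concept decision has no planned adjustment.

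At stake are a modest amount of power and the standing of any adjusted result. If an imbalance appears after unblinding and adjustment was only optional, an adjusted analysis would be read as chosen after the fact.

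**Working it through.** **Inputs from the protocol.** 132 FAS patients at 2:1, so 88 v 44; response 65% v 40%; two-sided alpha 0.10 (Sections 8.1 and 3.1.2.2).

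**Inputs assumed.** The protocol gives neither the prevalence nor the prognostic strength of any baseline factor. The checks use two independent binary factors, prevalence 50% each (also 20%/80%), and odds ratios for response from 1 to 4 per factor.

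**1. The plan's own power.**
- Pooled rate = (44 × 0.40 + 88 × 0.65)/132 = 0.567.
- Null SE = √[0.567 × 0.433 × (1/44 + 1/88)] = 0.0915, so significance needs an observed difference of about 1.645 × 0.0915 = 15.0 points.
- Alternative SE = √(0.40 × 0.60/44 + 0.65 × 0.35/88) = 0.0897.
- Power = Φ[(0.25 − 0.1505)/0.0897] = Φ(1.11) = 86.6%. Exact binomial enumeration gives 86.3%.

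The claim of more than 80% holds. Exact type I error with 44 and 88 patients is 9.7% to 10.2% for common response rates of 30% to 57%.

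**2. Chance imbalance without stratification.** SD of the between-arm difference in prevalence q = √[q(1 − q)(1/88 + 1/44)].
- q = 50%: SD 9.2 points. At least 10 points in either direction in about 28% of trials; at least 15 points in about 10%.
- q = 20%: SD 7.4 points. The same chances are about 18% and 4%.

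**3. What an imbalance does to the result.** With mean response near 50%, the response gap between factor levels is (√OR − 1)/(√OR + 1): 17.2 points at odds ratio 2 and 26.8 points at odds ratio 3. The gap is slightly smaller at other response rates. A 10-point imbalance therefore moves the observed difference by about 1.6 to 1.7 points (odds ratio 2) or 2.6 to 2.7 points (odds ratio 3). Compare the 15.0-point significance threshold and an SE of about 9 points.

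**4. Power with adjustment (simulated, 65% v 40%).** The second and third columns use 4,000 trials per row (simulation error about 0.5 point). The last two use 20,000 (about 0.25 point).

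| OR per factor | Chi-squared / CMH, 50% prevalence | Adjusted logistic, 50% | Chi-squared / CMH, 50%, repeat | Chi-squared / CMH, 20%/80% |
|---|---|---|---|---|
| 1 | 86.9 / 86.4 | 87.0 | 86.5 / 86.1 | not run |
| 1.5 | 85.7 / 86.1 | 86.5 | 86.1 / 86.3 | 86.2 / 85.9 |
| 2 | 86.3 / 87.3 | 87.7 | 86.4 / 87.7 | 86.4 / 87.3 |
| 3 | 86.3 / 89.5 | 90.0 | 86.5 / 89.5 | 85.9 / 87.8 |
| 4 | 87.1 / 91.6 | 92.1 | not run | not run |

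Simulated type I error was 9.4-10.1% for chi-squared, 9.7-10.7% for CMH and 10.1-11.0% for the logistic likelihood-ratio test.

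**The case against.** The strongest reply is that nothing is misstated. The test and the sample size agree, the power claim is met with room to spare, and the error rate is nominal. An unadjusted chi-squared test in a proof-of-concept trial is a legitimate choice. All of that stands.

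It also stands that the gain is uncertain. The protocol links neither baseline SLEDAI-2K nor Day 0 steroid use to SRI-4 response. With odds ratios of 1 to 1.5 there is no useful gain, and CMH may lose about half a point. Prevalence of 50% is a favourable case for both the power gain and the imbalance figures.

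A reader might infer that a damaging imbalance is likely and passes undiluted into the treatment difference. The figures do not support that: about 28% of trials, counting both directions, and a shift of under 3 points for a 10-point imbalance. The chi-squared test's type I error already allows for such chance differences.

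A reader might also infer that baseline steroid use is as strong a candidate as SLEDAI-2K. That is inference. Every patient must be at 10 mg/day or less before Day 0, and medication failure is triggered by what is taken after baseline.

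Finally, the absence of stratification is read from Section 3.2 naming no factor; the protocol never says that the list is unstratified, and an IWRS specification could hold more. What survives is narrower: the protocol itself fixes the primary test, and that test omits a baseline value that enters directly into the response definition.

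**Conclusion.** The point holds as a free improvement. The primary comparison is valid and adequately powered. It gives up some efficiency and protection against chance imbalance by not using baseline SLEDAI-2K. It would be wrong to conclude that the test is biased, that the trial is too small, or that baseline information is discarded altogether: Section 8 says covariates will be assessed, and Section 8.2.3 permits exploratory work.

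The likely gain runs from nothing (odds ratio 1 to 1.5 per factor), through about 1 point (odds ratio 2) and 3 to 4 points (odds ratio 3), to about 5 points (odds ratio 4). It is smaller when the factors are unevenly distributed. These figures rest on two assumed binary factors; adjusting for SLEDAI-2K alone would deliver only part of the gain. The case for SLEDAI-2K is firm because the endpoint is a fixed change in that score and almost nothing is lost if it proves non-prognostic. The case for steroid use is optional.

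**What to change.** Before unblinding, amend Section 8.2.3 (and the SAP to match) so that the primary comparison is a Cochran-Mantel-Haenszel test or a covariate-adjusted comparison, with an adjusted risk difference and its confidence interval. Adjust for baseline SLEDAI-2K, as a continuous covariate or at any cut fixed in advance, and optionally for oral corticosteroid use at Day 0 (yes/no). If a logistic likelihood-ratio test is preferred, note that its simulated error rate reached 11.0%, so CMH is the safer default at this size.

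Keep the unadjusted chi-squared test as a sensitivity analysis, which preserves the link to Section 8.1. Stratify the Phase 2 randomization list by the same factor only if the list is still open; otherwise adjust in the analysis alone.

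The cost is wording, plus an IWRS specification if the list can still be changed. No patients or data are added, and the loss of power if the factors turn out not to be prognostic is negligible (86.9% v 86.4%, within simulation error).
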